APPENDIX 1. SCHEDULE OF ASSESSMENTS

Visit	S1 ^{1,2}	S2	S3	T1	T2	T3/phone	T4	T5/EOS ³
Week	Wk -5	Wk -4	Wk -1	Wk 0	Wk 4	Wk 8	Wk 12	Wk 24
Procedure	Day -35± 7-63 to -29	Day -28±3	Day -7±3	Day 1	Day 29±3	Day 57±3	Day 85±3	Day 169±7
Informed Consent	X							
Enrollment Criteria	X							
Demographics	X							
Medical History	X							
Statin Intolerance Status Determination	X							
Concomitant Medications	X	X	X	X	X	X	X	X
Adverse Event Recording		X	X	X	X	X	X	X
Physical Exam		X						X
Weight ⁴	X			X			X	X
Height/BMI	X							
12-Lead ECG ⁵			X					X
Vital Signs ⁶	X	X	X	X	X		X	X
Serology ⁷	X							
Serum Pregnancy/FSH ⁸	X							
Urine Pregnancy ⁹				X				
TSH	X							
Clinical Safety Labs ¹⁰	X		X	X	X		X	X
Basic Fasting Lipids ¹¹	X		X	X	X		X	X
HbA _{1c}	X			X			X	X
10-mL reserve sample				X				X
PK Sample				X	X		X	X
Pharmacogenomics Sample (optional)				X				
apoB				X			X	X
hs-CRP				X			X	X
Diet and exercise counseling ¹²	X	X	X	X	X	X	X	
Establish Patient Eligibility		X		X				
Randomization				X				
IWRS Contact ^{12,13}	X	X		X			X	X
Single-blind Drug Dispensing		X						
Double-blind Drug Dispensing				X			X	
Drug Return/Compliance			X	X	X		X	X

NOTE: For patients who withdraw from study drug treatment, but consent to be followed for safety assessments and return to clinic for these visits, the visits will occur according to the protocol schedule. Safety assessments should include clinical safety and basic lipid laboratories (except for apoB and hs-CRP), adverse events (AEs), physical examination (PE), vital signs, and electrocardiograms (ECGs). ~~For patients who withdraw from study drug treatment, but consent to be followed for safety assessments by phone, the telephone contacts will occur according the protocol schedule with information regarding current health status and to collect information on AEs (eg, recent procedures, hospitalizations, and if the patient has died, the cause of death). If a patient does not provide consent to be followed for safety assessments per the protocol (either by returning to clinic or by phone), Visit T5 will be considered the End of Study (EOS)/Early Withdrawal from study and no further visits will be scheduled.~~

- ¹ An optional ~~basic-fasting~~ (minimum of 10 hours) **lipid TG assessment** MAY be completed **between Visit S1 and at** Visit S2 (prior to starting single-blind medication) if patient fails to meet ~~lipid TG~~ entry criterion at Visit S1. If this optional ~~basic-fasting lipid TG~~ is completed, the ~~mean of the first value and the repeat value~~ will be used to determine eligibility.
- ² A recheck of blood pressure may be completed **between Visit S1 and at** Visit S2 if the patient's DBP and/or SBP meet the exclusion criteria levels. Patients may randomize after blood pressure medications have been adjusted, the patients have been on stable doses of blood pressure medications for at least 2 weeks, and the repeat blood pressure values (diastolic blood pressure [DBP] and/or systolic blood pressure [SBP]) do not meet exclusionary values. Repeat labs may be completed at Visit S2 to determine eligibility if the patient's estimated glomerular filtration rate (eGFR), alanine aminotransferase (ALT), aspartate aminotransferase (AST) or other labs meet exclusion criteria levels. If this optional lab is completed, the repeated value will be used to determine eligibility.
- ³ All procedures will be completed for all patients at either EOS if completing the study or early withdrawal.
- ⁴ Body weight will be measured while fasting, using consistent scales, after voiding, and without shoes and outerwear (eg, coats).
- ⁵ Single 12-lead ECG will be performed prior to any blood sample collection.
- ⁶ Vital signs will include DBP, SBP, heart rate (HR) and will be collected prior to any blood sample collection. Patient will rest for 5 minutes prior to assessments.
- ⁷ Serology for HBsAg, HCV-ABVivi.
- ⁸ Pregnancy test completed in women of child-bearing potential only. FSH in naturally postmenopausal women ≥ 1 year without menses and < 55 years;
- ⁹ Urine pregnancy test completed in women of child-bearing potential only just prior to randomization.
- ¹⁰ Clinical safety labs include hematology, blood chemistry, and urinalysis at all visits. A coagulation panel will be completed for all patients at Week -5 (Visit S1). A coagulation panel will be completed only for patients on anti-coagulant therapy at Day 1 (Visit T1) and 3 to 5 days later. **For these visits, the sample may be analyzed at either the central or a local lab.** Please refer to laboratory manual for detailed schedule of tests.
- ¹¹ Basic fasting (minimum of 10 hours) lipids include total cholesterol, calculated low-density lipoprotein cholesterol (LDL-C), high-density lipoprotein cholesterol (HDL-C), non-HDL-C, and triglycerides. ~~Repeat within 1 week if exceed protocol specified criteria.~~
- ¹² Diet and exercise counseling per local and/or regional guidelines for the management of hyperlipidemia.
- ¹³ Interactive web response system (IWRS) contact at either an early withdrawal or an EOS visit to register study discontinuation visit date.

CHANGE 37 REMOVAL OF DATE WITHIN THE BODY OF APPENDIX 2 PAGES

Location:

Appendix 2: Final Date, all pages within Appendix 2

Original text:

Final Date: 25 August 2016

New text:

~~**Final Date:** 25 August 2016~~

[figure not shown]
CHANGE 38 SPONSOR'S SIGNATORY CHANGES

Location:

**MODIFICATION HISTORY**

Unique Identifier for this Version	Date of the Document Version	Author	Significant Changes from Previous Authorized Version
1.0	07FEB2017		Not Applicable – First Version
1.1	07MAR2017		Changes requested from client, first review. Added appendices for multiple imputation method, AESIs and list of TLF for DMC.
1.2	14APR2017		Changes requested from client, second review.
1.3	24MAY2017		Changes requested from client, added new tables.
1.4	10OCT2017		Make relevant changes from reviews of 047 and 048 SAPs and shells.
1.5	7JAN2018-28FEB2018		Make Esperion’s changes resulting from review of 048 dry run and 046 dry run of TLF.
1.6	14MAR2018		Final changes from Esperion
1.7	21MAR2018		Add additional analysis for hsCRP

[Redacted]

Version Number: 1.7  
 Version Date: 21Mar2018

[Redacted]

## LIST OF ABBREVIATIONS

ADaM	Analysis Data Model
AE	Adverse Event
AESI	Adverse Event of Special Interest
ANCOVA	Analysis of Covariance
apoB	Apolipoprotein B
ATC	Anatomical Therapeutic Chemical
BLQ	Below Limit of Quantification
Bpm	Beats per Minute
C	Celsius
CAS	Completer Analysis Set
CEC	Clinical Endpoints Committee
CI	Confidence Interval
cm	Centimeters
CV	Cardiovascular; coefficient of variation
CVD	Cardiovascular Disease
DBP	Diastolic Blood Pressure
dL	Deciliters
DMC	Data Monitoring Committee
ECG	Electrocardiogram
eCRF	Electronic Case Report Form
eGFR	Estimated Glomerular Filtration Rate
FAS	Full Analysis Set
HDL-C	High-density Lipoprotein – Calculated
HR	Heart Rate
hsCRP	High-sensitivity C-reactive Protein
IMP	Investigational Medicinal Product
ITT	Intention-to-treat

[REDACTED]

Version Number: 1.7  
 Version Date: 21Mar2018

[REDACTED]

LIST OF ABBREVIATIONS (cont'd)

kg	kilograms
LDL-C	Low-density Lipoprotein – Calculated
LDL-M	Low-density Lipoprotein - Measured
LMT	Lipid-modifying Therapy
LSM	Least Squares Mean
LTFU	Lost to Follow-up
m	Meters
MACE	Major Adverse Cardiac Events
MedDRA	Medical Dictionary for Regulatory Activities
mg	Milligrams
MI	Myocardial Infarction
min	Minutes
PK	Pharmacokinetics
PMM	Pattern Mixture Model
PT	Preferred Term
SAF	Safety Analysis Set
SAP	Statistical Analysis Plan
SD	Standard Deviation
SE	Standard Error
SBP	Systolic Blood Pressure
SI	Systeme International
SOC	System Organ Class
STDM	Study Data Tabulation Model
TC	Total Cholesterol
TEAE	Treatment-emergent Adverse Event

[Redacted]

[figure not shown]
Version Number: 1.7  
 Version Date: 21Mar2018

[Redacted]

LIST OF ABBREVIATIONS (cont'd)

TG	Triglycerides
ULN	Upper Limit of Normal
ULQ	Upper Limit of Quantification
US	United States
WHO-DDE	World Health Organization – Drug Dictionary Enhanced
Yrs	Years

---

 Version Number: 1.7  
Version Date: 21Mar2018

## 1. INTRODUCTION

This document describes the rules and conventions to be used in the presentation and analysis of efficacy and safety data for Protocol 1002-046. It describes the data to be summarized and analyzed, including specifics of the statistical analyses to be performed.

This statistical analysis plan (SAP) is based on the original protocol version dated August 25, 2016 and amendment 1 dated March 27, 2017.

## 2. STUDY OBJECTIVES

### 2.1. PRIMARY OBJECTIVE

The primary objective is to assess the 12-week efficacy of bempedoic acid 180 mg/day versus placebo in decreasing low-density lipoprotein cholesterol (LDL-C) in statin intolerant patients with elevated LDL-C.

### 2.2. SECONDARY OBJECTIVES

The secondary objectives are:

- To evaluate the effect of 24-week treatment with bempedoic acid 180 mg/day versus placebo on LDL-C.
- To evaluate the effect of bempedoic acid 180 mg/day versus placebo on non-high-density lipoprotein cholesterol (non-HDL-C), total cholesterol (TC), high-sensitivity C-reactive protein (hs-CRP), and apolipoprotein B (apoB) after 12 weeks of treatment.
- To evaluate the 24-week safety and tolerability of bempedoic acid 180 mg/day compared to placebo.

### 2.3. TERTIARY OBJECTIVE

[REDACTED]

[REDACTED]

Version Number: 1.7  
 Version Date: 21Mar2018

[figure not shown]
[REDACTED]

### 3. STUDY DESIGN

#### 3.1. GENERAL DESCRIPTION

This is a Phase 3, randomized, double-blind, placebo-controlled, parallel group multicenter study that will be conducted at approximately 71 clinical sites in North America. Screening Week -5 (Visit S1) will be approximately 5 weeks prior to randomization. Eligible patients will return to the clinical site at Week -4 (Visit S2) to initiate administration of single-blind (patient only) placebo study drug. Eligible patients will return at Week -1 (Visit S3) for lipid and safety laboratories and an assessment of tolerability and study drug adherence. Approximately 300 patients with a history of statin intolerance (SI) will be stratified based on patient type (primary prevention; secondary prevention) and randomized at Week 0 (Visit T1) in a 2:1 ratio to receive either bempedoic acid 180 mg (n = 200) or matching placebo (n = 100) once daily for 24 weeks. Randomized patients will return for clinic visits at Week 4 (Visit T2), Week 12 (Visit T4), and Week 24 (Visit T5). A phone visit will occur at Week 8 (Visit T3).

Figure A 1002-046 Study Design

#### 3.2. SCHEDULE OF EVENTS

The schedule of events can be found in [Section 8.3](#) of the protocol.

[Redacted]

Version Number: 1.7  
 Version Date: 21Mar2018

[Redacted]

## 4. PLANNED ANALYSES

The following analyses will be performed for this study:

- Safety analyses for Data Monitoring Committee (DMC) meetings
- Final Analysis

### 4.1. DATA MONITORING COMMITTEE (DMC)

The subset of outputs for the DMC is listed in [Appendix 3](#). Access to results will be provided by Quintiles in a separate unblinding plan.

### 4.2. FINAL ANALYSIS

All final, planned analyses identified in this SAP will be performed by Quintiles Biostatistics following Sponsor Authorization of this Statistical Analysis Plan, Database Lock, Sponsor Authorization of Analysis Sets and Unblinding of Treatment.

## 5. ANALYSIS SETS

Agreement and authorization of subjects included/ excluded from each analysis set will be conducted prior to the unblinding of the study.

### 5.1. SAFETY ANALYSIS SET [SAF]

The Safety Analysis Set (SAF), used for all of the safety summaries, is defined as all randomized patients who received at least 1 dose of double-blind study medication. Patients in the SAF will be included in the treatment group that they actually received, regardless of their randomized treatment.

### 5.2. FULL ANALYSIS SET [FAS]

The Full Analysis Set (FAS), used for all of the efficacy analyses, is defined as all randomized patients. The FAS is also known as the intention-to-treat (ITT) set of patients. Patients in the FAS will be included in their randomized treatment group, regardless of the treatment they actually received.

[REDACTED]

Version Number: 1.7  
 Version Date: 21Mar2018

[REDACTED]

### 5.3. COMPLETER ANALYSIS SET [CAS]

The Completer Analysis Set (CAS), used for all the primary, and secondary efficacy analysis, is defined as patients who completed IMP treatment per the end of treatment CRF page and have non-missing week 12 LDL-C value.

### 5.4. PK ANALYSIS SET [PKS]

The PK Analysis Set will include all subjects in the safety analysis set who have at least one non-missing PK assessment. These subjects will be evaluated for PK concentration summaries unless major protocol deviations are identified during the protocol deviation review or if key dosing or sampling information is missing.

## 6. GENERAL CONSIDERATIONS

### 6.1. REFERENCE START DATE AND STUDY DAY

Study Day will be calculated from the reference start date, and will be used to show start/ stop day of assessments and events.

Reference start date is defined as the day of the first dose of study medication (Day 1 is the day of the first dose of study medication). In case the first dose date is missing, randomization date will be used instead.

If the date of the event is on or after the reference date then:

$$\text{Study Day} = (\text{date of event} - \text{reference date}) + 1.$$

If the date of the event is prior to the reference date then:

$$\text{Study Day} = (\text{date of event} - \text{reference date}).$$

In the situation where the event date is partial or missing, the date will appear partial or missing in the listings, and Study Day, and any corresponding durations will be presented based on the imputations specified in [Appendix 2: Partial Date Conventions](#).

### 6.2. BASELINE

Unless otherwise specified, baseline is defined as the last non-missing measurement taken prior to

[REDACTED]

Version Number: 1.7  
 Version Date: 21Mar2018

[REDACTED]

Visit Windows	$[-\infty, -32]$	$[-31, -18]$	$[-17, -1]$	$[1, 1]$	$[2, 43]$	$[44, 71]$	$[72, 127]$	$[128, \infty]$
----------------------	------------------	--------------	-------------	----------	-----------	------------	-------------	-----------------

## 6.5. STATISTICAL TESTS

The default significance level will be (5%); confidence intervals will be 95% and all tests will be two-sided, unless otherwise specified in the description of the analyses.

## 6.6. COMMON CALCULATIONS

For quantitative measurements, change from baseline will be calculated as:

- Test Value at Visit X – Baseline Value

Percent change from baseline will be calculated as:

- $[(\text{Test Value at Visit X} - \text{Baseline Value}) / \text{Baseline Value}] \times 100$

[figure not shown]
## 6.7. SOFTWARE VERSION

All analyses will be conducted using SAS version 9.4 or higher.

# 7. STATISTICAL CONSIDERATIONS

## 7.1. SAMPLE SIZE

The primary efficacy endpoint for this study is the percent change from baseline to Week 12 in LDL-C.

## 7.2. ADJUSTMENTS FOR COVARIATES AND FACTORS TO BE INCLUDED IN ANALYSES

The following covariates and factors are used in the analyses. For details of their inclusion in the models, see the specific analysis section.

- treatment group (bempedoic acid 180 mg/day; placebo)
- baseline laboratory value of interest
- CVD risk category (primary prevention; secondary prevention)
- treatment by subgroup interaction term for subgroup analyses of efficacy variables

## 7.3. MULTICENTER STUDIES

This study will be conducted by multiple investigators at multiple centers in North America.

## 7.4. MISSING DATA

Missing efficacy data will be handled as described in [section 18.1.2](#) of this analysis plan.

## 7.5. MULTIPLE COMPARISONS/ MULTIPLICITY

In terms of controlling the overall Type I error rate, a gatekeeping or stepdown approach will be used to test the primary efficacy endpoint and then specific secondary efficacy endpoints sequentially in order to preserve the study-wise Type I error rate. The sequence for the stepdown procedure in this study is as follows:

1. Test the primary efficacy endpoint: percent change from baseline to Week 12 in LDL-C
2. Test the percent change from baseline to Week 24 in LDL-C
3. Test the percent change from baseline to Week 12 in non-HDL-C
4. Test the percent change from baseline to Week 12 in TC
5. Test the percent change from baseline to Week 12 in apoB
6. Test the percent change from baseline to Week 12 in hsCRP

In this hierarchical testing structure, each hypothesis is tested at a significance level of 0.05, two-sided. Statistical significance at each step is required in order to test the next hypothesis. If the primary endpoint meets the criteria for statistical significance, then the percent change from

[REDACTED]

[figure not shown]
Version Number: 1.7  
 Version Date: 21Mar2018

[REDACTED]

baseline to Week 24 in LDL-C will be tested; and so forth.

## 8. OUTPUT PRESENTATIONS

[Appendix 1](#) shows conventions for presentation of data in outputs.

The templates provided with this SAP describe the presentations for this study and therefore the format and content of the summary tables, figures and listings to be provided by  Biostatistics.

## 9. DISPOSITION AND WITHDRAWALS

All patients who were screened will be accounted for in this study. Reasons for screen failure will be summarized by pre-defined categories per CRF. For screen failure due to inclusion and exclusion criteria, the criteria category will be presented. Patient disposition and withdrawals (both from study treatment and the study), will be presented for the FAS. The number of patients in each analysis set will be presented for all randomized patients.

## 10. PROTOCOL DEVIATIONS

All protocol deviations will be provided in a listing with type and description. Major protocol deviations will be summarized by treatment group. The protocol deviations are recorded and tracked in the trial monitoring platform CTMS.

## 11. DEMOGRAPHIC AND OTHER BASELINE CHARACTERISTICS

Demographic data and other baseline characteristics will be presented for the FAS and CAS. No statistical testing will be carried out for demographic or other baseline characteristics. The following demographic and other baseline characteristics will be reported for this study:

- Age (years) - calculated relative to date of randomization
- Age category (<65 years vs. ≥65 years and < 75 years vs. ≥75 years)
- Gender
- Race
- Ethnicity
- CVD risk category (primary prevention; secondary prevention)
- Region (US vs. Canada)
- Weight (kg)
- Height (cm)

Version Number: 1.7  
 Version Date: 21Mar2018

- BMI (kg/m^2)
- BMI category (< 25 vs. 25 - < 30 vs. ≥ 30 kg/ m^2)
- Baseline Laboratory Results (Total Cholesterol, LDL-C, HDL-C, Triglycerides, Non-HDL-C, ApoB, and hsCRP)
- Baseline LDL-C category (<130 mg/dL, ≥130 and < 160 mg/dL, or ≥160 mg/dL)
- Background lipid modifying therapy use (Statin vs. Non-statin vs. None)
- History of diabetes (Yes vs. No)
- History of hypertension (Yes vs. No)
- Baseline Vital Signs (systolic blood pressure (SBP), diastolic blood pressure (DBP) and heart rate (HR))
- Alcohol consumption
- Tobacco use

### 11.1. DERIVATIONS

- Age (years) = (date of randomization – date of birth)/365.25
- BMI (kg/ m^2) = weight (kg)/ height (m)

## 12. MEDICAL AND SURGICAL HISTORY

Medical and Surgical History information will be presented by MedDRA SOC (System Organ Class) and PT (Preferred Term) for the FAS. Medical History conditions are defined as those conditions which stopped prior to or at Screening. Medical and Surgical History will be coded using MedDRA Version 20.1.

## 13. CONCOMITANT ILLNESSES

Concomitant Illnesses will be presented by SOC (System Organ Class) and PT (Preferred Term) for the FAS. Concomitant Illnesses are conditions (other than the indication being studied) which started prior to the date of randomization and are ongoing at the date of randomization. Concomitant Illnesses will be coded using MedDRA Version 20.1.

## 14. CARDIOVASCULAR HISTORY/RISK FACTORS

Cardiovascular history/risk factors collected at screening will be presented in a table by treatment group and in a data listing.

Version Number: 1.7  
 Version Date: 21Mar2018

## 15. MEDICATIONS

Prior and concomitant medications will be presented for the SAF and coded using the September 2017 version of the World Health Organization Drug Dictionary Enhanced (WHO-DDE). Tables excluding lipid-modifying therapies will be presented.

Prior and concomitant lipid modifying therapy including statin (less than low dose) and others will be tabulated and listed separately. See protocol [section 7.3.1](#) for the list of LMT allowed in the study.

Medications will be summarized by ATC classification and preferred term by treatment group.

See [Appendix 2](#) for handling of partial dates for medications, in the case where it is not possible to define a medication as prior or concomitant to treatment, the medication will be classified by the worst case, i.e. concomitant.

Prior medications are medications which started and stopped prior to the first dose of double-blind study medication.

Concomitant medications are medications that patients are taking at the time of first dose of double-blind medication or started during the study, which means: started prior to, on or after the first dose of double-blind study medication and no later than 30 days following the end of study medication, and ended on or after the date of first dose of study medication or were ongoing at the end of the study.

### 15.1. BASELINE BACKGROUND LIPID MODIFYING THERAPY

Baseline background Lipid modifying therapy is defined as any lipid modifying agents that are ongoing at the time of randomization. It will be presented in separate tables and listings by category (as defined in protocol section 7.3.1) and coded medication name and by treatment group.

## 16. ADDITIONAL POST-RANDOMIZATION ADJUNCTIVE LIPID-LOWERING THERAPY

The number and percent of patients in each treatment group requiring additional (post-randomization) lipid-lowering therapy will be summarized by treatment group as well as provided in a listing. The lipid-lowering therapy includes all post-randomization concomitant medications based on ATC class 2 = lipid-modifying agent.

Version Number: 1.7  
 Version Date: 21Mar2018

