8.4. Early Withdrawal from Study or Treatment

Patients who withdraw from study drug prior to Week 24 (Visit T5) for any reason will be asked to continue to be followed for safety assessments, including basic fasting lipids, at clinic visit following the protocol-specified visit schedule (see [Section 8.3](#)).

Patients who temporarily withdraw from study drug prior to Week 24 (Visit T5) for any reason may restart study drug providing that 1) the patient and the investigator are in agreement regarding this course of action, 2) the patient has been off of study drug for 4 weeks or less; and 3) study drug can be started as soon as possible. For cases where the patient has been off of study drug for more than 4 weeks, the investigator must contact the medical monitor for approval prior to restarting study drug.

Patients who do not wish to continue to return to the clinic for safety assessments will be asked to participate in phone calls from the site at protocol-specified visits (see [Section 8.3](#)), or at a minimum at 24 weeks, to collect information on AEs, concomitant medications, and current health status.

The patient's decision to participate in the clinical study is voluntary. Patients may refuse to continue in the study and/or withdraw from participation in this study at any time, for any reason, specified or unspecified, and without penalty or loss of benefits to which the patient is otherwise entitled.

It is the right and duty of the Investigator to interrupt the treatment of any patient whose health or well-being may be threatened by continuation in this study. Such patients should be withdrawn from the study and should not be continued under a modified regimen.

Patients who are withdrawn from the study may not re-enter. The reasons for withdrawal from this study or treatment may include:

- Patient's withdrawal of consent
- Failure to comply with the protocol
- Lost to follow-up
- Illness, condition, or procedural complication (including AEs) affecting the patient's ability to participate or requiring prohibited medication
- The Sponsor or Investigator terminates the study
- In the Investigator's judgment, it is deemed in the best interest of the patient to discontinue his/her participation in the study
- Any other reason

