18.2.3.2. Adjunctive Lipid-modifying Therapy (LMT) Analysis

To explore the potential impact from adjunctive lipid-modifying therapy use during the study, a sensitivity analysis will be performed for primary and key secondary endpoints using data prior to the change of the post-baseline LMT only, i.e., lab test date  $\leq$  change date of LMT. There will be no imputation for missing data.

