## APPENDIX 2. PARTIAL DATE CONVENTIONS

Imputed dates will NOT be presented in the listings.

Algorithm for Treatment Emergence of Adverse Events:

START DATE	ACTION
Known and AESTART=study med start date	If AEPRIOR=Y then not TEAE If AEPRIOR=N then TEAE
Known and AESTART>or < study med start date	If start date < study med start date, then not TEAE If start date > study med start date and <=study med end date + 30 , then TEAE
Partial	If AEPRIOR=Y then not TEAE Otherwise, If Impute 1 st of month if date is missing; impute 1 st of Jan if both date and month are missing. If resulting imputed start date is prior to study med start date, set as study med start date. If imputed start date is <= study med end date + 30 days, then TEAE; otherwise NOT TEAE
Missing	If AEPRIOR=Y then not TEAE Otherwise, Assumed TEAE

Algorithm for Prior / Concomitant Medications:

Please note that the study med start date is the double-blind med start date.

START DATE	STOP DATE	ACTION
Known	Known	If stop date < study med start date, assign as prior If stop date >= study med start date and start date <= end of treatment, assign as concomitant If stop date >= study med start date and start date > end of treatment, assign as post study

START DATE	STOP DATE	ACTION
	Partial	Impute stop date as latest possible date (i.e. last day of month if day unknown or 31 st December if day and month are unknown), then: If stop date < study med start date, assign as prior If stop date >= study med start date and start date <= end of treatment, assign as concomitant If stop date >= study med start date and start date > end of treatment, assign as post treatment
	Missing	If stop date is missing could never be assumed a prior medication If start date <= end of treatment, assign as concomitant If start date > end of treatment, assign as post treatment
Partial	Known	Impute start date as earliest possible date (i.e. first day of month if day unknown or 1 st January if day and month are unknown), then: If stop date < study med start date, assign as prior If stop date >= study med start date and start date <= end of treatment, assign as concomitant If stop date >= study med start date and start date > end of treatment, assign as post treatment

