	Partial	Impute start date as earliest possible date (i.e. first day of month if day unknown or 1 st January if day and month are unknown) and impute stop date as latest possible date (i.e. last day of month if day unknown or 31 st December if day and month are unknown), then: If stop date < study med start date, assign as prior If stop date >= study med start date and start date <= end of treatment, assign as concomitant If stop date >= study med start date and start date > end of treatment, assign as post treatment
	Missing	Impute start date as earliest possible date (i.e. first day of month if day unknown or 1 st January if day and month are unknown), then: If stop date is missing could never be assumed a prior medication If start date <= end of treatment, assign as concomitant If start date > end of treatment, assign as post treatment
Missing	Known	If stop date < study med start date, assign as prior If stop date >= study med start date, assign as concomitant Cannot be assigned as 'post treatment'
	Partial	Impute stop date as latest possible date (i.e. last day of month if day unknown or 31 st December if day and month are unknown), then: If stop date < study med start date, assign as prior If stop date >= study med start date, assign as concomitant Cannot be assigned as 'post treatment'

Version Number: 1.7  
 Version Date: 21Mar2018

START DATE	STOP DATE	ACTION
	Missing	Assign as concomitant

---

[REDACTED]

Version Number: 1.7  
Version Date: 21Mar2018

[REDACTED]

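### The added lipid-therapy table counts only concomitant drugs, the SAP defines that class in two conflicting ways, and neither window covers the off-drug follow-up that supplies lipid values to Week 24

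*SAP*

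**What the plan says.** SAP Section 16 sets out to report, by arm, the patients who need additional lipid-lowering therapy after randomization, then limits which drugs qualify: "The lipid-lowering therapy includes all post-randomization concomitant medications based on ATC class 2 = lipid-modifying agent". Whether a drug is counted therefore depends on the meaning of concomitant, which the SAP gives in two places.

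- **Section 15:** a drug can be concomitant if it starts "no later than 30 days following the end of study medication".
- **Appendix 2, medication algorithm:** no 30-day allowance. With a known start and a missing stop, the rule is "If start date > end of treatment, assign as post treatment". With both dates known it is "If stop date >= study med start date and start date > end of treatment, assign as post study". The rows for partial dates use the same end-of-treatment cut-off.

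Protocol Section 8.4 says that patients who stop study drug early "will be asked to continue to be followed for safety assessments, including basic fasting lipids" on the normal visit schedule. SAP Section 5.2 defines the FAS as everyone randomized. SAP Appendix 4 sets out cohorts 7 and 8 for patients who are off treatment but have a Week 12 value.

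SAP Section 18.2.3.2 adds an LMT sensitivity analysis "using data prior to the change of the post-baseline LMT only, i.e., lab test date" on or before the date on which LMT changed. It names no source for that date.

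**The concern.** The Section 16 table and the Section 18.2.3.2 analysis are the two planned outputs aimed specifically at added lipid therapy. To be useful, the table should cover the same period as the efficacy samples. It does not: the concomitant class ends at, or 30 days after, the end of study drug, while LDL-C sampling can continue to Week 24.

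The conflict between the two definitions is a separate problem. Two programmers following the SAP could classify the same ezetimibe record differently and produce different tables. At stake is the completeness of a by-arm description that a reader would use to judge whether added therapy influenced LDL-C.

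**Working it through.** The plan gives no figure to reproduce, so the check applies the two rules to example dates.

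**Inputs.** Nominal Week 12 sample, Day 85 (Protocol 8.3.7, ±3 days). Nominal Week 24 sample, Day 169 (Protocol 8.3.8, ±7 days). Section 15: concomitant if start ≤ last dose + 30. Appendix 2: concomitant if start ≤ end of treatment. The SAP does not define end of treatment; I take it as the last dose date.

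**Step 1: one patient, last dose Day 29.**

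| New agent starts | Days after last dose | Section 15 | Appendix 2 |
|---|---|---|---|
| Day 30 | 1 | concomitant | not concomitant |
| Day 50 | 21 | concomitant | not concomitant |
| Day 59 | 30 | concomitant | not concomitant |
| Day 60 | 31 | not concomitant | not concomitant |
| Day 70 | 41 | not concomitant | not concomitant |

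The rules disagree for starts on Days 30 to 59. From Day 60 both leave the agent out.

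**Step 2: start days that go uncounted, up to and including the visit day.** Appendix 2: visit day − last dose. Section 15: visit day − last dose − 30, with a floor of 0.

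| Last dose | Week 12, Appendix 2 | Week 12, Section 15 | Week 24, Appendix 2 | Week 24, Section 15 |
|---|---|---|---|---|
| Day 1 | 84 | 54 | 168 | 138 |
| Day 29 | 56 | 26 | 140 | 110 |
| Day 57 | 28 | 0 | 112 | 82 |
| Day 85 | – | – | 84 | 54 |

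Under Section 15, an omission before the nominal visit needs a last dose by 85 − 31 = Day 54 (Week 12) or 169 − 31 = Day 138 (Week 24).

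**Step 3: whether the matching lipid values are analysed.** They are. An observed off-drug value belongs to Appendix 4 cohort 7 or 8 and enters the FAS analysis. Those cohorts also feed imputation: cohort 8 for bempedoic acid patients missing a value while on drug, and cohort 7 for those missing a value off drug.

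**Step 4: an inconsistency within Appendix 2.** A drug with no start date can never be classed as post treatment; if its stop date is missing, or is on or after the study drug start, it is concomitant. An undated agent thus stays in the class while one properly dated after the last dose drops out.

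**Step 5: how many patients.** The documents give no rates. Purely as an assumption, suppose 5–20% stop before Week 12 and 20–50% of those start another agent and still give lipids. With 200 and 100 patients per arm, that is 200 × 0.05 × 0.20 = 2 to 200 × 0.20 × 0.50 = 20 on bempedoic acid, and 1 to 10 on placebo. These counts assume the Appendix 2 rule; Section 15 would miss fewer.

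**The case against.** **Section 15 is the definition, and Appendix 2 only handles partial dates.** Section 15 does cite Appendix 2 for partial dates, and under Section 15 an agent started two weeks after stopping would be counted. But the Appendix 2 algorithm has an explicit row for two known dates, so the conflict is real. Starts after 30 days are lost even under Section 15.

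**Other analyses already deal with these patients.** This largely stands. The on-treatment analysis (SAP 18.2.3.3) drops samples taken more than 7 days after the last dose. The completer analysis (SAP 5.3 and 18.2.3.1) requires completed study treatment. Both cover the primary and key secondary endpoints. They remove off-drug values as a whole, however, so they cannot separate the effect of added therapy from that of stopping drug.

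**Late add-on therapy may be rare.** This is possible. Post-randomization lipid results are masked (Protocol 6.3), which removes the study laboratory as a trigger. The one named adjunctive pathway, for high triglycerides, begins on treatment (Protocol 10.2.12) and would be counted. A reader might infer that patients who stop drug are those most likely to start another agent; the documents do not show this. Equally, the prohibited list in Protocol 7.3.2 does not name ezetimibe or fenofibrate.

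**The LMT sensitivity analysis may be unaffected.** This is a fair reading. Section 18.2.3.2 cuts at a change date and mentions neither concomitant status nor Section 16. A reader might infer that it inherits the same gap, but the text does not establish that. What stands is that the source of the date is unstated.

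**Conclusion.** The point holds as a defect in a descriptive table and an undefined input to one sensitivity analysis. The two definitions conflict over starts 1 to 30 days after the last dose, and neither counts a dated start beyond 30 days, although lipids are collected to Week 24 and kept in the FAS. Because following the rules as written gives contradictory and incomplete counts, this is a faulty rule and not merely missing detail.

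Three stronger readings are not supported.

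- **That the primary result is biased by this rule.** Relabelling a medication changes no primary estimate or p-value. Assumed rates of 10% stopping, 50% of those adding an agent and a −20% effect would move an arm mean by 0.10 × 0.50 × 20 = 1.0 percentage point, but that movement is already in the FAS estimate however the drug is classed.
- **That a difference between arms in discontinuation would go unseen.** Disposition is summarized by treatment group (Protocol 11.4), and withdrawals from study treatment are presented for the FAS (SAP Section 9).
- **That affected values remain in the Section 18.2.3.2 analysis.** This would follow only if its change dates use the concomitant flag.

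The day counts assume that end of treatment means last dose and that visits fall on nominal days. The number of patients affected is unknown.

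**What to change.** 1. Align the Appendix 2 cut-off with Section 15 for the general medication tables, and define end of treatment.
2. In Section 16, count any lipid-modifying agent started, or background agent changed, from randomization through the patient's last study visit, whether or not the patient is still on study drug. Tabulate by arm, split into while on study drug and after stopping.
3. In Section 18.2.3.2, state that the LMT change dates come from this same set.

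The cost is SAP wording, one derived flag and a re-tabulation. No new data are needed: Protocol 7.3 requires concomitant medication to be recorded throughout the study, and Protocol 8.4 and 8.4.1 include it in follow-up after withdrawal. The adjunctive-therapy counts may rise slightly.
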